7.0 ADVERSE EVENTS

This study will be conducted in compliance with the Data Safety Monitoring Plan (DSMP) of the Robert H. Lurie Comprehensive Cancer Center of Northwestern University (please refer to <http://cancer.northwestern.edu/cro/data/DataandSafetyMonitoringPlanMay2014.pdf>). The level of risk attributed to this study requires high intensity monitoring, as outlined in the DSMP. In addition, the study will abide by all safety reporting regulations, as set forth in the Code of Federal Regulations and as required by the NCI.

7.1 Adverse Event Monitoring

Adverse event data collection and reporting, which are required as part of every clinical trial, are done to ensure the safety of subjects enrolled in the studies as well as those who will enroll in future studies using similar agents. Adverse events are reported in a routine manner at scheduled times during a trial (see Section 5 for timepoints). In addition, certain adverse events must be reported in an expedited manner to allow for optimal monitoring and patient safety and care.

All patients experiencing an adverse event, regardless of its relationship to study drug, will be followed until:

- the adverse event resolves or the symptoms or signs that constitute the adverse event return to baseline;
- any abnormal laboratory values have returned to baseline;
- there is a satisfactory explanation other than the study drug for the changes observed; or
- death.

7.2 Definitions & Descriptions

7.2.1 Adverse Event

An adverse event (AE) is any untoward medical occurrence in a patient receiving study treatment and which does not necessarily have a causal relationship with this treatment. An AE can therefore be any unfavorable and unintended sign (including an abnormal laboratory finding), symptom, or disease temporally associated with the use of an experimental intervention, whether or not related to the intervention.

Recording of AEs should be done in a concise manner using standard, acceptable medical terms. In general, AEs are not procedures or measurements, but should reflect the reason for the procedure or the diagnosis based on the abnormal measurement. Preexisting conditions that worsen in severity or frequency during the study should also be recorded (a preexisting condition that does not worsen is not an AE). Further, a procedure or surgery is not an AE; rather, the event leading to the procedure or surgery is considered an AE.

If a specific medical diagnosis has been made, that diagnosis or syndrome should be recorded as the AE whenever possible. However, a complete description of the signs, symptoms and investigations which led to the diagnosis should be provided. For example, if clinically significant elevations of liver function tests are known to be secondary to hepatitis, "hepatitis" and not "elevated liver function tests" should be recorded. If the cause is not known, the abnormal test or finding should be recorded as an AE, using appropriate medical terminology (e/g/ thrombocytopenia, peripheral edema, QT prolongation).

7.2.2 **Severity of AEs**

All non-hematologic adverse events will be graded according to the NCI Common Terminology Criteria for Adverse Events (CTCAE) version 4.0. The CTCAE v4 is available at <http://ctep.cancer.gov/reporting/ctc.html>

If no CTCAE grading is available, the severity of an AE is graded as follows:

- Mild (grade 1): the event causes discomfort without disruption of normal daily activities.
- Moderate (grade 2): the event causes discomfort that affects normal daily activities.
- Severe (grade 3): the event makes the patient unable to perform normal daily activities or significantly affects his/her clinical status.
- Life-threatening (grade 4): the patient was at risk of death at the time of the event.
- Fatal (grade 5): the event caused death.

7.2.3 **Serious Adverse Events (SAEs)**

All SAEs, regardless of attribution, occurring from time of signed informed consent, through 30 days after the last administration of study drug, must be reported upon discovery or occurrence.

An SAE is defined in regulatory terminology as any untoward medical occurrence that:

- **Results in death.**
If death results from (progression of) the disease, the disease should be reported as event (SAE) itself.
- **Is life-threatening.**

The patient was at risk of death at the time of the event; it does not refer to an event that hypothetically might have caused death if it were more severe.

- **Requires in-patient hospitalization or prolongation of existing hospitalization for \geq 24 hours.**
- **Results in persistent or significant disability or incapacity.**
- **Is a congenital anomaly/birth defect.**
- **Is an important medical event.**

Any event that does not meet the above criteria, but that in the judgment of the investigator jeopardizes the patient, may be considered for reporting as a serious adverse event. The event may require medical or surgical intervention to prevent one of the outcomes listed in the definition of "Serious Adverse Event".

For example: allergic bronchospasm requiring intensive treatment in an emergency room or at home; convulsions that may not result in hospitalization; development of drug abuse or drug dependency.

7.2.4 **Unanticipated Problems Involving Risks to Subject or Others**

A UPIRSO is a type of SAE that includes events that meet ALL of the following criteria:

- Is *unanticipated* in terms of nature, severity, or frequency
- Places the research subject or others at a different or *greater risk of harm*
- Is deemed to be *at least possibly related* to participation in the study.

7.3 **Adverse Event Reporting**

7.3.1 **Routine Reporting**

All routine adverse events, such as those that are expected, or are unlikely or definitely not related to study participation, are to be reported on the appropriate eCRF according to the time intervals noted in the appendices. Routine AEs will be reviewed by the Data Monitoring Committee (DMC) according to the study's phase and risk level, as outlined in the DSMP.

7.3.2 **Determining if Expedited Reporting is Required**

This includes all events that occur within 30 days of the last dose of protocol treatment. Any event that occurs more than 30 days after the last dose of treatment and is attributed (possibly, probably, or definitely) to the agent(s) must also be reported accordingly.

- 1) Identify the type of adverse event using the NCI CTCAE v 4.0.
- 2) Grade the adverse event using the NCI CTCAE v 4.0.
- 3) Determine whether the adverse event is related to the protocol therapy. Attribution categories are as follows:
 - Definite: AE is clearly related to the study treatment.
 - Probable: AE is likely related to the study treatment.
 - Possible: AE may be related to the study treatment.
 - Unlikely: AE not likely to be related to the study treatment.
 - Unrelated: AE is clearly NOT related to the study treatment.
- 4) Determine the prior experience of the adverse event. Expected events are those that have been previously identified as resulting from administration of the agent. An adverse event is considered unexpected, for expedited reporting purposes only, when either the type of event or the severity of the event is not listed in:
 - the current protocol
 - the current Investigator's Brochure

7.3.3 **Expedited Reporting of SAEs/Other Events**

7.3.3.1 Reporting to the Northwestern University QAM/DMC

All SAEs must be reported to the assigned QAM within 24 hours of becoming aware of the event. Completion of the NU CRO SAE Form is required.

The completed form should assess whether or not the event qualifies as a UPIRSO. The report should also include:

- Protocol description and number(s)
- The patient's identification number
- A description of the event, severity, treatment, and outcome (if known)
- Supportive laboratory results and diagnostics
- The hospital discharge summary (if available/applicable)

All SAEs will be reported to, and reviewed by, the DMC at their next meeting.

7.3.3.2 Reporting to the Northwestern University IRB

The following information pertains to the responsibilities of the lead site (Northwestern University). Additional participating sites should follow their local IRB guidelines for reporting to their local IRBs.

- Any death of an NU subject that is unanticipated in nature and at least possibly related to study participation will be promptly reported to the NU IRB within 24 hours of notification.
- Any death of an NU subject that is actively on study treatment (regardless of whether or not the event is possibly related to study treatment)
- Any death of a non-NU subject that is unanticipated and at least possibly related and any other UPIRSOs will be reported to the NU IRB within 5 working days of notification.
- All other deaths of NU subjects not previously reported, other non-NU subject deaths that were unanticipated and unrelated, and any other SAEs that were not previously reported as UPIRSOs will be reported to the NU IRB at the time of annual continuing review.

7.3.3.3 Reporting to the FDA

All notifications to the FDA will be handled centrally the QA team at Northwestern.

The FDA will be notified within 7 calendar days of any SAE that is associated with study treatment, is unexpected, and is fatal or life-threatening.

The FDA will be notified within 15 calendar days of any SAE that is associated with the study treatment, unexpected, and serious but *not fatal or life-threatening*. This includes any previous SAEs that were not initially deemed reportable, but are later determined to meet the criteria for reporting (i.e. by the DMC).

All other SAEs will be reported on an annual basis as part of the annual FDA report.

7.3.3.4 Reporting to Takeda

Regardless of expectedness or causality, all SAEs must also be reported to Takeda or designee:

- **Fatal and Life Threatening SAEs** within 24 hours but no later than 4 calendar days from observation or awareness of the event
- **All other serious (non-fatal/non-life threatening) events** within 4 calendar days of observation or awareness of the event

The NU CRO SAE report form will be completed and submitted for all SAEs requiring reporting to Takeda. Reports will include event term(s), serious criteria, intensity of the event(s), and causality of the event(s). Follow-up information on the SAE may be requested by Takeda.

The NU PI is responsible to ensure that the SAE reports are sent to Takeda (or designee) from all sites participating in the study. Sub-investigators must report all SAEs to the NU CRO QAM (as outlined above). NU must also provide Takeda with a copy of all communications with applicable regulatory authorities related to the study product(s) as soon as possible but no later than 4 calendar days of such communication.

The contact for reporting is:

Takeda or Designee

SAE and Pregnancy Reporting Contact Information

[contact]

Email: [contact]

If a woman becomes pregnant or suspects that she is pregnant while participating in this study, she must inform the investigator and NU CRO QAM immediately and permanently discontinue study drug. The QAM must fax a completed Pregnancy Form to Takeda or designee. The pregnancy must be followed for the final pregnancy outcome.

If a female partner of a male patient becomes pregnant during the male patient's participation in this study, the QAM must also immediately fax a completed Pregnancy Form Takeda or designee. Every effort should be made to follow the pregnancy for the final pregnancy outcome.

A product complaint is a verbal, written, or electronic expression that implies dissatisfaction regarding the identity, strength, purity, quality, or stability of a drug product. Individuals who identify a potential product complaint situation should immediately contact MedComm Solutions (see below) and report the event. Whenever possible, the associated product should be maintained in accordance with the label instructions pending further guidance from a Takeda Quality representative.

For Product Complaints, call MedComm Solutions at:

[contact] ([name])

Product complaints in and of themselves are not AEs. If a product complaint results in an SAE, an SAE form should be completed and sent to Takeda.

8.0 DRUG INFORMATION

8.1 Alisertib

8.1.1 Other names MLN8237

8.1.2 Classification - type of agent

Alisertib is an adenosine triphosphate (ATP)-competitive and reversible inhibitor of Aurora A kinase.

8.1.3 Mode of action

Consistent with the mechanism of action for an Aurora A kinase inhibitor, alisertib treatment results in formation of abnormal mitotic spindles, an accumulation of mitotic cells, and a decrease in the proliferation of a broad range of tumor cell lines grown in culture.

8.1.4 Storage and stability

Tablets should remain in the bottle provided until use. The container should be stored at the investigative site at controlled room temperature (20-25°C; 68-77°F; excursions are permitted from 15-30°C; 59-86°F) and used before the retest expiry date provided by Takeda. Containers should be kept closed during storage. Patients should be instructed on proper storage, accountability, and administration of alisertib, including that alisertib is to be taken as intact tablets.

8.1.5 Protocol dose specifics

The starting dose for patients on both arms will be 50 mg orally BID; each day the doses must be taken at least 6 hours apart, with or without food.

8.1.6 Preparation

No preparation is necessary for drug used in this study. Alisertib is an investigational agent and therefore should be handled with due care. In case of contact with broken tablets, raising dust should be avoided during the cleanup operation. The product may be harmful by inhalation, ingestion, or skin absorption. Gloves and protective clothing should be worn during preparation and the cleanup operation. The area should be ventilated and the spill site washed after material pick-up is complete. The spilled material should be disposed of as hazardous medical waste in compliance with federal, state, and local regulations. In case of contact with the powder (eg, from a broken tablet), skin should be washed immediately with soap and copious amounts of water for at least 15 minutes. In case of contact with the eyes, copious amounts of water should be used to flush the eyes for at least 15 minutes. Medical personnel should be notified.

8.1.7 Route of administration for this study

Oral. Patients will be instructed to take each oral dose of alisertib with 8 ounces (1 cup, 240 mL) of water. All tablets are to be ingested whole; patients who have difficulty swallowing tablets will be excluded from the study.

8.1.8 Incompatibilities

Patients should not drive, operate dangerous tools or machinery, or engage in any other potentially hazardous activity that requires full alertness and coordination if they experience sedation while enrolled in this study.

Patients should be instructed to limit the use of alcohol while enrolled in this study. Patients should consume no more than 1 standard unit of alcohol per day during the study and for 30 days from the last dose of alisertib. A standard unit of alcohol is defined as a 12 oz beer (350 mL), 1.5 oz (45 mL) of 80-proof alcohol, or one 6-oz (175 mL) glass of wine.

8.1.9 Availability & Supply

Alisertib will be provided by Takeda and will be supplied as 10 mg ECT, with the dose strength expressed as milligrams of active drug (free acid). Alisertib ECT are packaged in a 60-cc high density polyethylene (HDPE) bottle with a rayon

coil, induction seal, desiccant packs, and a polypropylene child resistant cap. Patients will be instructed on the home use of alisertib, including the requirement that alisertib be administered as intact tablets.

8.1.10 **Side effects**

Common

In prior clinical trials, the following have been considered as emerging as a consequence of the treatment in $\geq 10\%$ of patients:

- Gastrointestinal Disorders
 - Diarrhea
 - Nausea
 - Stomatitis
 - Vomiting
 - Constipation
 - Abdominal discomfort
- Hematological abnormalities
 - Neutropenia
 - Anemia
 - Thrombocytopenia
 - Febrile neutropenia
- General abnormalities
 - Fatigue
 - Fever
 - Edema
 - Asthenia
 - Infection, even in absence of neutropenia (including thrush)
- Dermatological abnormalities
 - Alopecia
 - Rash
- Nervous system disorders
 - Somnolence
 - Headache
 - Dizziness
 - Difficulty walking
 - Psychiatric illness
 - Confusional state/disorientation
- Metabolic/Nutritional consequences
 - Dehydration
 - Decreased appetite
 - Low potassium and blood magnesium levels
- Respiratory disorders
 - Cough
 - Difficulty breathing

In prior clinical trials, there have been also been reports of eye disorders (not further specified), muscle/joint disorders (back and extremity pain), and vascular disorders (low blood pressure, sometimes severe (“shock”))

Less common (occurring between 1% and 10% of the time):

- Liver function test abnormalities

Infrequent (occurring less than 1% of the time):

- Cardiac abnormalities have been reported in 2 patients, including reduced cardiac function, and abnormal heart rhythm (QTc prolongation)

8.1.11 **Nursing implications**

Antiemetogenic agents may be administered at the discretion of the investigator. Neutralizing antacids and calcium-containing supplements cannot be taken from 2 hours prior to alisertib dosing until up to 2 hours after dosing.

9.0 CORRELATIVE STUDIES

9.1 Sample Collection

Blood and/or bone marrow samples for PD studies will be collected at multiple timepoints for cycles 1-6. Samples will be collected at the time of routine blood and/or bone marrow collection on Day 1 of each cycle. Sample collection on Day 15 will be optional. For MF patients, only peripheral blood samples will be collected unless bone marrow is deemed medically necessary; AMKL patients may include both blood and bone marrow procurement. Approximately 25 ml of peripheral blood and 10-20 ml of bone marrow will be collected in lavender top EDTA tubes and dark green top tubes respectively, and labeled with the patient initials, study number, and date of collection. Samples may sit at room temperature until they are picked up or shipped.,.

As mentioned above, correlative bone marrow samples should be obtained any time bone marrows are collected as clinically indicated during study participation. At baseline, bone marrow collection is not required for study entry, but study team should request 3-4 unstained slides from prior bone marrow testing performed within the last year. Unstained slides should be shipped at room temperature to [name]

It is strongly preferred that correlative samples be collected and shipped only on Monday – Thursday (with same day shipment preferred). Friday collections/shipments should be avoided to ensure sample stability. Since these samples are collected on Day 1 of each cycle, it is preferred that Day 1 visits be conducted on Monday through Thursday when correlative samples are being collected. Sites should use the available windows to achieve this. Please contact the QAM if there are any questions.

9.2 Transport/Shipment

Samples will be picked up by [name] lab (for NU samples) or shipped at room temperature by overnight courier to [name] laboratory (for University of Miami and Mayo Clinic specimens). Samples will be shipped the day of collection(preferred), or within the week after collection in the event that additional samples will be collected from other patients in the same week. Samples will only be sent Monday through Thursday. Any samples collected between Thursday late afternoon and Sunday night will be shipped on Monday morning.

ATTN: [name] Laboratory
Northwestern University
[name]
[name]
Chicago, IL 60611

The phone number to contact [name] lab for questions or to confirm receipt of samples is [contact]. Alternatively, [name] may be reached via email at [contact].

9.3 Processing and Analysis

Upon receipt, monocuclear cells will be collected from the samples by Ficoll preparation. Aliquots of the cells will be used in the following ways:

1. To extract RNA for gene expression studies. We will determine the pathways that are up or down-regulated upon Alisertib treatment. We anticipate changes in cell cycle regulatory and megakaryocyte differentiation pathways.

2. To isolate proteins for analysis of levels of key factors, such as transcription factors, ribosome assembly proteins, and signaling molecules. We will use western blot assays to determine the changes that occur with Alisertib treatment.
3. To perform flow cytometry will be performed to analyze the state of maturation of the cells, including CD41, CD42 expression and DNA content. We will use FlowJo software to analyze the flow cytometry data to determine the levels of these differentiation parameter.
4. To perform flow cytometry to assess the state of signaling cascades, such as the AKT, ERK, and STAT pathways. We will use FlowJo software to analyze the flow cytometry data to determine the levels of activation of these pathways.
5. To perform flow cytometry to assess the hematopoietic stem cell compartment. We will use FlowJo software to determine the different populations of hematopoietic stem and progenitor populations.
6. To culture in vitro and in vivo to assess the state and differentiation potential of hematopoietic progenitor cells.
7. We may elect to use samples at a later time point to directly compare differences in gene expression and signaling pathways from sequential patient specimens. Thus, we will freeze down aliquots of cells, and/or or RNA, and/or protein for future cell culture, flow cytometry, DNA, RNA and protein extractions. Samples will be kept for up to two years.
8. An optional correlative study (separate patient consent) will involve exome or whole genome sequencing on normal and tumor DNA for patients with AMKL. DNA from tumor samples will be available as in line 7 above; to obtain germline DNA, buccal swabs will be obtained.

Samples will be labeled with a number and not the patient names. Identifying information will be retained by the PI and co-investigators and not shared with the laboratory staff. Identities of the subjects will not be reported in presentations or publications.

Samples will be retained indefinitely in [name] laboratory located at Northwestern University.

Please refer to laboratory manual for more details.

10.0 STATISTICAL CONSIDERATIONS

10.1 Statistical Analysis

10.1.1 Primary Endpoint

The primary objective of this pilot study is to determine the safety profile. All adverse events (AEs) will be summarized using frequencies and percentages. These percentages will be subclassified by type of AE, timing of AE in the treatment cycle, frequency and attribution of AEs (treatment related or not).

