2.0 OBJECTIVES & ENDPOINTS

2.1 Primary Objective & Endpoint

The primary objective of this pilot study is to determine the safety profile of alisertib in patients with AMKL and in patients with MF.

Adverse events will be defined according to the National Cancer Institute's Common Terminology Criteria for Adverse Events (NCI CTCAE) version 4.0. The number, frequency, and severity of adverse events will be recorded every cycle for each population. All patients who receive at least 1 dose of alisertib will be considered evaluable for this endpoint.

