4.0 TREATMENT PLAN

4.1 Overview

This will be a two arm pilot study of alisertib treatment in patients with AMKL or MF. The starting dose (level 1) for all patients will be 50 mg BID, administered orally on days 1-7 of each cycle (1 cycle = 21 days), based on the MTD from previous studies. Patients may continue to receive cycles of alisertib until progression of disease or unacceptable toxicity. There will be no long-term follow-up beyond end of treatment, aside from a standard end of treatment visit approximately 30 days after the last dose of study drug, followed by a final off-study visit approximately 6 months after the last dose. Patients with on-going adverse events will be followed until resolution of the event(s), defined as a return to baseline or stabilization of the event.

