4.7 Duration of Follow Up

Once off treatment for any reason, patients will have an end-of-treatment visit at approximately 30 days after their last dose of alisertib. Patients who are experiencing on-going toxicities at this time will continue to be followed until resolution of the toxicity (either return to baseline or stabilization). In addition, there will be a final off-study visit approximately 6 months after the last dose of treatment to assess for late-onset toxicity.

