- ^m Beyond Cycle 6, if the patient's condition is stable, then they will be required to come in only on Day 1 of every even cycle (every 6 weeks) for study visit. In that case, for those visits when patient is not coming to clinic for study visit, CBC and CMP only will be done in an outside laboratory convenient for the patient, and results will have to be faxed to the clinic. Patients can start their treatment at home only after the treating physician has reviewed the laboratory results and determined that they are able to continue treatment. For these cycles, the study coordinator will contact the patient on/prior to Day 1 to inform them if they can or cannot start the new cycle, and also check compliance regarding study drug intake.
- ⁿ Patients will be administered orally on days 1-7 of each cycle (1 cycle = 21 days); patients may remain on treatment until development of unacceptable toxicity or progression of disease.
- ^o Patients will have an end of treatment (EOT) visit approximately 30 days (+10 days) after the last dose of treatment; if a bone marrow was carried out at disease progression, this will be considered the EOT marrow and does not need to be repeated at the EOT visit.
- ^p Patients will have a final end of study (EOS) visit approximately 6 months (+/- 30 days) after the last dose of treatment to assess for late-onset toxicity.

^q Labs required only on days 1 and 15 of cycles 2-6, but in the event of cycle 1 toxicity or at treating investigator's discretion, additional interim labs may be performed per standard of care.

^r Baseline Medical History within 14 days of registration

^s Baseline ECOG Status within 14 days of registration.

^t Baseline Hematology, Chemistry, DIC screen, Pregnancy Test, within 14 days of registration

^u Baseline Adverse Events and Concomitant Medications within 14 days of registration.

^v Informed consent should be obtained within 28 days of registration.

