6.0 ENDPOINT ASSESSMENT

6.1 Primary Endpoint

The primary objective of this pilot study is to determine the safety profile of alisertib in patients with AMKL and in patients with MF.

Adverse events will be defined according to the National Cancer Institute's Common Terminology Criteria for Adverse Events (NCI CTCAE) version 4.0. The number, frequency, and severity of adverse events will be recorded every cycle for each population. All patients who receive at least 1 dose of alisertib will be considered evaluable for this endpoint.

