10.2 Sample Size and Accrual

MF and AMKL are rare diseases with total prevalence (total number of patients with the disease in the US at any time) under 15,000. NIH considers prevalence under 200,000 a rare disease. A total of 24 subjects (maximum 24 subjects, regardless of the disease breakdown of MF or AMKL. If all 24 were MF, that would be acceptable) will be accrued to this trial. Approximately 4 potentially eligible patients are seen per month at all sites, and it is anticipated that at least 1 per month will be accrued, leading to a 2 year accrual period.

. Approximate standard errors for the estimated response rate when the true response rate is 10% are +/- 6% with a sample of 24 patients total, +/- 18% with a sample of 18 patients, +/- 9% with 12 patients and +/- 10% to 12% with 6 patients. In the event that a patient consents and is registered to the study but never begins treatment, that patient may be replaced. The QAM must be notified and, if necessary, DMC approval must be obtained.

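### Primary adverse event percentages are planned without intervals, a fixed window or a number at risk per cycle, although treatment is uncapped and a disease group may be very small

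*Combined protocol and SAP*

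**What the plan says.** The primary objective is the safety profile in AMKL and in MF (Sections 2.1 and 6.1). The analysis in Section 10.1.1 is brief: "All adverse events (AEs) will be summarized using frequencies and percentages", and "These percentages will be subclassified by type of AE, timing of AE in the treatment cycle", by frequency and by attribution.

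The population is defined elsewhere: "All patients who receive at least 1 dose of alisertib will be considered evaluable for this endpoint" (Section 6.1; Sections 2.1 and 4.3 agree). On collection, "The number, frequency, and severity of adverse events will be recorded every cycle for each population" (Section 2.1).

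The length of treatment is open: "Patients may continue to receive cycles of alisertib until progression of disease or unacceptable toxicity" (Section 4.1). After treatment, "there will be a final off-study visit approximately 6 months after the last dose of treatment to assess for late-onset toxicity" (Section 4.7), and both schedules of events list adverse events at that visit.

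Section 10.2 caps the total at 24, leaves the disease split free and accepts that all could be MF. Response, the secondary endpoint, is given an exact binomial 95% interval in Section 10.1.2 and precision figures in Section 10.2. Section 10.1.1 has no counterpart to either.

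**The concern.** Two gaps matter for a trial whose main product is a safety description.

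The first is exposure. With no window stated, the natural reading is that a patient counts if the event occurs at any time from first dose to the last visit. A patient on drug for many cycles then has more opportunity for an event than one who stops after two. If the two diseases differ in time on drug, their percentages will differ even at equal risk per cycle. The split by timing does not settle this, because Section 10.1.1 does not say whether its denominator is everyone ever treated or those still being treated.

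The second is precision. Section 1.6 justifies the pilot by the lack of safety data in these two diseases and by a possible differentiation syndrome. Seeing no case of that syndrome in a handful of AMKL patients is a plausible and important result. Under the plan it would be tabulated as 0% with no statement of the risk that it leaves open.

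**Working it through.** **Inputs from the protocol.** Denominator: patients with at least one dose (2.1, 4.3, 6.1). Maximum n: 24, split open (10.2). Treatment length: no cap (4.1, 4.6). Interval method in use: exact binomial, for response only (10.1.2). The protocol gives no expected number of cycles for either disease, so cycle counts and per-cycle risks below are assumptions, shown as a range.

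**Step 1: the plan's own precision figures.** These are standard errors for the response rate at a true rate of 10%, SE = √(0.10 × 0.90 / n):

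| n | Computed SE | Stated in 10.2 |
|---|---|---|
| 24 | 6.1% | 6% |
| 18 | 7.1% | 18% |
| 12 | 8.7% | 9% |
| 6 | 12.2% | 10% to 12% |

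The figure for n=18 does not reproduce. That is a separate matter about response, and nothing below depends on it. No precision figure is given for adverse events.

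**Step 2: what zero events leaves open.** The exact two-sided 95% upper limit for 0 of n is 1 − 0.025^(1/n). The chance of seeing no event when the true risk is 10% is 0.9^n.

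| n | Upper limit for 0 events | Chance of 0 events at 10% risk |
|---|---|---|
| 24 | 14.2% | 8.0% |
| 18 | 18.5% | 15.0% |
| 12 | 26.5% | 28.2% |
| 6 | 45.9% | 53.1% |

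**Step 3: the effect of unequal exposure.** With a constant per-cycle risk h over k cycles, the crude percentage is 1 − (1 − h)^k. For illustration, every patient in one group receives 2 cycles and every patient in the other receives 8:

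| Per-cycle risk, same in both | 2 cycles | 8 cycles |
|---|---|---|
| 2% | 4.0% | 14.9% |
| 5% | 9.8% | 33.7% |
| 10% | 19.0% | 57.0% |

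**Step 4: durations that vary between patients.** Let the number of cycles be geometric with mean m and q = 1/m. The crude percentage is then 1 − q(1 − h) / [1 − (1 − q)(1 − h)]. At h = 10%:
- m = 2: 1 − 0.45/0.55 = 18.2%.
- m = 8: 1 − 0.1125/0.2125 = 47.1%.

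The gap narrows but stays large.

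**Step 5: would a longer window cure it?** Counting events through cycle 6 in all treated patients still compares, for example, 2 cycles with 6. At 10% risk that is 19.0% against 1 − 0.9^6 = 46.9%. Only cycle 1 is started by every patient in the safety population.

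**Step 6: ascertainment after cycle 6.** The MF schedule (5.1, footnote m) has stable patients attend "only on Day 1 of every even cycle (every 6 weeks) for study visit". Section 4.2 names odd cycles instead. The two must be reconciled, but both give 6-week spacing. The AMKL schedule (5.2) keeps an exam on day 1 of each cycle. Late-cycle adverse events may therefore be picked up at different intervals in the two diseases.

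**The case against.** The other side has several good points.

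- **A denominator exists.** A reader might infer that the percentages have none. Three sections define it as all patients with at least one dose. What is unspecified is the number at risk per cycle or the exposure time.
- **Silence is not a wrong plan.** Section 10.1.1 does not say that percentages run over whole treatment courses, nor that the timing split ignores who was still on treatment. Adverse events are recorded every cycle by population, so a sensible table could be built without breaching the text. This stands; the point is that the plan leaves the choice open.
- **No disease contrast is planned.** Nothing in Section 10.1 tests MF against AMKL, and patients are grouped by diagnosis. Crude incidence per treated patient is a valid description of each group, and a reader who knows n can work out the limit for zero events. It would be too strong to say that the results cannot be read.
- **The durations are not documented.** Section 1.1.1 describes a poor outlook in AMKL, and the MF schedule foresees patients stable beyond cycle 6. Yet both arms require a life expectancy of at least 6 months, and no section gives expected cycles. A sharp difference in time on drug is plausible, not established.
- **Risk may not be constant.** Section 4.3 reduces the dose after toxicity with no re-escalation. If risk falls after early cycles, the gap in Step 3 shrinks.

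These limit the claim but do not close the gap. The descriptive design does not explain the missing interval, because response is equally descriptive and has one.

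**Conclusion.** The point holds as a cheap and worthwhile improvement to the primary analysis. Section 10.1.1 plans only crude percentages per treated patient, without an interval, a fixed window, a number at risk per cycle or an explicit split by disease.

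The precision part rests on no assumption beyond group size: zero events is compatible with a true risk of up to 14.2% at n=24 and 45.9% at n=6. The exposure part is illustrative. At 2 against 8 cycles and a constant, equal risk of 2% to 10% per cycle, crude percentages would range from 4% against 15% to 19% against 57%. The direction holds whenever exposure is unequal and some risk persists beyond the early cycles; the size depends on assumptions that the protocol does not supply.

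The consequence is for how the two safety profiles are described and read side by side. The documents do not support the stronger readings that the endpoint lacks a denominator, that a planned comparison is biased, or that crude incidence is uninterpretable.

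**What to change.** Amend Section 10.1.1 to report, for each disease:

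1. Patients with an event over patients treated, with exact binomial 95% intervals (the method already in 10.1.2). Restrict the intervals to key categories such as grade 3 or higher, serious, treatment-related and differentiation syndrome.
2. The same for cycle 1 as the fixed window. State its end in days, because Section 4.3 allows the next cycle to be delayed.
3. Incidence by cycle of onset, with the number of patients starting that cycle as denominator, plus the distribution of cycles received.

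Keep the all-cycle percentage alongside these. Do not use a window through cycle 6 as the fixed window, since it still mixes unequal exposure. Footnote the by-cycle tables with two cautions: later cycles describe only patients still on treatment, and stable MF patients may be seen only every 6 weeks after cycle 6.

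The cost is a few sentences and tables from data already recorded every cycle for each population. The intervals will be wide: 1 of 6 gives 0.4% to 64.1%. That width is information that the reader of a small pilot needs.
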